10 MONITORING AND MANAGEMENT OF ECG-RELATED ABNORMALITIES

The definition of a cardiac dysrhythmia characterized by a CTCAE Version 5 grading for electrocardiogram QT corrected interval prolonged is presented in [Table 3](#).

Table 3 CTCAE Version 5 Grading for Electrocardiogram QT Corrected Interval Prolonged

CTCAE Term	Grade 1	Grade 2	Grade 3	Grade 4
Electrocardiogram (ECG) QT Corrected Interval Prolonged	Average QTc 450 – 480 msec	Average QTc 481 – 500 msec	Average QTc ≥ 501 msec ; or ≥60 msec change from baseline	Torsade de pointes; polymorphic ventricular tachycardia; signs/symptoms of serious arrhythmia

Any participant who experiences a treatment-emergent QT interval corrected for heart rate (QTc) prolongation of Grade 2 or higher must return to the study site for prompt clinical evaluation after the abnormal ECG results become available and to repeat the safety ECG assessment. A PK sample must be obtained at the same visit that the repeat ECG assessment is performed, and the date and time of the PK draw and the last dose of study drug (and that of pirfenidone or nintedanib, if applicable) must be recorded in the eCRF.

- Grade 2 QTcF interval > 480 but ≤ 500 msec; or increased > 30 to ≤ 60 msec from baseline value → **The participant must return to the study site within 48 to 72 hours.**
- Grade 3: QTcF interval > 500 msec or increased > 60 msec from baseline value → **The participant must return to the study site within 24 hours or, if not feasible, to a local clinic or hospital for immediate clinical evaluation.**

Clinical evaluation must include the following:

- Ruling out comorbidities and potential risk factors (eg, congestive heart failure, bradyarrhythmias)
- Evaluation of electrolyte disturbances (eg, potassium, calcium, and magnesium)
- Review of potential concomitant medications known to prolong the QTc interval (eg, serotonin receptor antagonists, anti-emetics)

If prompt evaluation is not feasible (as described above and based on severity of abnormality), study drug should be interrupted immediately (date of last study drug dose [and that of pirfenidone or nintedanib, if applicable] must be recorded in the eCRF), and the participant must return to the study site as soon as possible for

re-evaluation. The Sponsor Study Director should be notified within 48 hours of the availability of initial ECG results and/or assessment of clinical symptoms.

Study drug must be permanently discontinued in the event of QTc prolongation meeting the following criteria:

- Confirmed Grade 3 abnormality: QTcF interval > 500 msec or increased > 60 msec from baseline value
- Grade 4 abnormality (does not require confirmation): torsade de pointes; polymorphic ventricular tachycardia; signs/symptoms of serious arrhythmia

All treatment-emergent QTc abnormalities meeting the criteria for permanent discontinuation (as listed above) must be reported to the Sponsor Study Director within 48 hours. The participant must permanently discontinue study drug immediately and continue to be followed for close monitoring and causality and clinical evaluation as follows:

- Repeat ECG at least once weekly until abnormalities stabilize (ie, QTc interval is comparable to baseline value or baseline grade of abnormality, if applicable) and the participant is asymptomatic
- Correction of any electrolyte abnormalities, if applicable
- Obtain a detailed history of symptoms and comorbidities
- Obtain a history of concomitant drug use (including nonprescription or over-the-counter medications and herbal and dietary supplement preparations)
- Consider a cardiology consultation

For participants with confirmed QTc prolongation (as described below) warranting temporary interruption of study drug but not meeting permanent drug discontinuation criteria, more frequent ECG testing and clinical assessments (at least once weekly) must be performed using unscheduled visits, including a thorough causality evaluation and in consultation with the Sponsor Study Director.

- Confirmed Grade 2 QTcF interval > 480 but ≤ 500 msec
- Confirmed increased > 30 to ≤ 60 msec from baseline value

Re-initiation of study drug can only be considered if a more likely etiology is identified and if ECG abnormalities have returned to baseline values. **The decision to restart study drug must be discussed and approved in consultation with the Sponsor Study Director prior to re-initiation.** More frequent clinical monitoring and ECG assessments (at least once weekly) after re-initiation of study drug, if applicable, should be performed through use of

unscheduled visits. **If the QTc prolongation reoccurs upon re-challenge, study drug must be permanently discontinued.**

Any participant who experiences a QTc prolongation not confirmed upon repeat ECG assessment may continue or resume administration of study drug and follow the scheduled study visits, if clinically appropriate. More frequent clinical evaluation and ECG monitoring through use of unscheduled visits is allowed, if clinically warranted.

Participants who permanently discontinue study drug due to potential QTc prolongation must be followed for close monitoring until abnormalities stabilize to baseline levels or baseline grade of abnormality and the participant is asymptomatic. Participants should be encouraged to remain in the study and completed all scheduled visits and assessments. Long-term follow-up information should be provided for participants who permanently discontinue drug due to confirmed QTc prolongation, including information on corrective therapy and cardiology consultation, if applicable.

11 **EARLY DISCONTINUATION OF STUDY OR INDIVIDUAL PARTICIPANTS**

In accordance with the Declaration of Helsinki, participants have the right to withdraw from the study at any time for any reason. The Investigator or Sponsor may withdraw a participant from the study or discontinue study drug for any of the following reasons:

- Noncompliance with protocol procedures including those relating to administration of study drug
- A serious or intolerable AE occurs
- Infection with COVID-19 that precludes safe participation in the study
- A clinically significant change in a laboratory parameter occurs
- Confirmed elevations in serum ALT or AST meeting criteria for suspected acute DILI (see [Section 9](#))
- Prolonged ECG QTc interval meeting criteria for permanent discontinuation (see [Section 10](#))
- Male participants whose female partners become pregnant during the study must stop the medication immediately
- The Sponsor or Investigator terminates the study
- The participant requests to be discontinued from the study

If a participant is withdrawn from the study or discontinues study drug, they will undergo early termination assessments; refer to the Schedule of Events ([Appendix 1](#)).

12 PLANNED STATISTICAL METHODS

12.1 General Considerations

This is an exploratory study, with exploratory efficacy and biomarker assessments; as such, no statistical hypotheses are being tested. In general, data will be summarized using statistical summary methods; graphic presentations of data may also be prepared. A statistical analysis plan (SAP), prepared and agreed before final database lock, will describe the analytic approach and methods in more detail.

12.2 Determination of Sample Size

The sample size of approximately 12 participants (8 participants receiving 160 mg PLN-74809 and 4 receiving placebo) is expected to provide a meaningful evaluation of PLN-74809 safety, tolerability and PK in the target population, and add to the data of approximately 21 participants planned to be evaluated at this dose level in an ongoing multicenter, dose ranging Phase 2a study (PLN-74809-IPF-202).

12.3 Analysis Populations

Safety Population: All randomized participants who receive at least one dose of study drug will be included in the safety analyses.

PK Analysis Population: All randomized participants who have sufficient PLN-74809 concentration data for PK calculation will be included in the PK analyses.

PD Analysis Population: All randomized participants who receive any amount of study drug and who have results from Baseline and from at least one post-baseline PET/MRI scan or PD assessment will be included in the PD analyses.

12.4 Demographics and Baseline Characteristics

Data will be summarized using statistical summary methods.

12.5 Primary Endpoints

12.5.1 Primary Pharmacodynamic Endpoint

- Quantification of type 1 collagen in the lung following 12 weeks of treatment, as assessed by changes from Baseline in ^{68}Ga -CBP8 PET/MRI tracer uptake patterns.

If a participant elects to withdraw from the study after the 6th week of randomization, an end of participation ^{68}Ga -CBP8 PET/MRI will be offered to the participant to enhance appropriate data capture.

PET/ MRI

PET/MRI scans will be interpreted by American Board of Nuclear Medicine (ABNM)-certified nuclear medicine physicians in an unblinded manner. Lung contours will be generated from baseline and post-treatment PET/MRI. Mean and maximum standardized uptake value (SUV) measurements of contoured lungs will be calculated using MIMS software, by analyzing the uptake values of ^{68}Ga -CBP8 PET/MRI within the lung, and by comparing values from the baseline and post-treatment scans. Numerical and graphical results will be presented by dose.

In addition, relationships between PK and type 1 collagen deposition, as well as between MRI and PET imaging, may be evaluated in an exploratory fashion and presented in a graphical manner (see [Section 12.7.1](#)).

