Statistical Methods:	
Analysis Populations
 
Safety Population: All randomized participants who receive at least one dose of study drug will be included in the safety analyses.
 
PK Analysis Population: All randomized participants who have sufficient PLN-74809 concentration data for PK calculation will be included in the PK analyses.
 
PD Analysis Population: All randomized participants who receive any amount of study drug and who have results from Baseline and from at least one post-baseline PET/MRI scan or PD assessment will be included in the PD analyses.
 
Primary Endpoint: PD
 
Quantification of type 1 collagen in the lung following 12 weeks of treatment, as assessed by changes from Baseline in ^{68}Ga-CBP8 PET/MRI tracer uptake patterns.
 
PET/MRI scans will be interpreted by American Board of Nuclear Medicine (ABNM)-certified nuclear medicine physicians in an unblinded manner. Lung contours will be generated from baseline and post-treatment PET/MRI. Mean and maximum standardized uptake value (SUV) measurements of contoured lungs will be calculated using MIMS software, by analyzing the uptake values of ^{68}Ga-CBP8 PET/MRI within the lung, and by comparing values from the baseline and post-treatment scans. Numerical and graphical results will be presented by dose.
 
In addition, relationships between PK and type 1 collagen deposition, as well as between MRI and PET imaging, may be evaluated in an exploratory fashion and presented in a graphical manner
 
Secondary Endpoint: Safety
 
Safety data from all participants who received at least one dose of study drug will be incorporated into the final safety analysis.
 
Exploratory Endpoints
 
PK and PD
 
Plasma PLN-74809-versus-time profiles (with plasma concentrations on both a log and linear scale) will be plotted for each participant. Non-compartmental analysis will be used to calculate PK parameters as appropriate.
 
Relationships between PK and type 1 collagen deposition, as well as between MRI and PET imaging, may be evaluated in an exploratory fashion and presented in a graphical manner.

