3 INVESTIGATIONAL PLAN

3.1 Overall Study Design and Plan

This is a Phase 2a, single-center, randomized, double-blinded, placebo-controlled study to evaluate type 1 collagen deposition in the lungs following once-daily (QD) treatment with 160 mg PLN-74809 for 12 weeks in participants with IPF.

The study consists of an up to 28-day screening period, a 12-week treatment period, and a 2-week (± 3 days) post treatment follow-up period.

Potential participants who provide written informed consent will be screened for study eligibility up to 28 days before administration of the first dose of study drug. Approximately 12 eligible participants will be randomized in a 2:1 ratio (160 mg PLN-74809 vs placebo; 8 receiving PLN-74809 and 4 receiving placebo) on Day 1 (Visit 3). Study treatment will be administered once daily for 12 weeks. Randomization will be stratified by use of standard of care (SoC) IPF therapy with pirfenidone or nintedanib (SoC use; yes or no).

^{68}Ga -CBP8 PET/MRI scans will be conducted within 7 days prior to baseline and at or within 7 days prior to Week 12, as indicated in the Schedule of Events ([Appendix 1](#)).

Participants who discontinue study drug for safety reasons prior to completion of 12 weeks of treatment will be encouraged to remain in the study to complete all remaining assessments; if this is not feasible, they will be asked to return to the clinic for an Early Termination (ET) visit for follow-up evaluations. If a participant elects to withdraw from the study after the 6th week of randomization, an end of participation ^{68}Ga -CBP8 PET/MRI will be offered to the participant to enhance appropriate data capture.

Potential acute exacerbations, respiratory-related hospitalizations, and/or respiratory-related deaths will be reviewed by an adjudication committee.

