3.2 Rationale for PLN-74809 Doses and Control Group

This study will quantify type 1 collagen expression in the lung following PLN-74809 exposure, as assessed by changes from baseline in ^{68}Ga -CBP8 PET/MRI tracer uptake patterns following 12 weeks of treatment with 160 mg of PLN-74809, administered once daily. Available safety, tolerability and PK data from Study PLN-74809-104 and Study PLN-74809-IPF-202 (i.e., Part B evaluating 40 mg once daily for 12 weeks; Part C has initiated and will evaluate doses of 80 or 160 mg once daily, in parallel groups) support evaluation of a dose of 160 mg, which is expected to achieve the target 80% inhibitory concentration (IC₈₀) for $\alpha_v\beta_6$ and $\alpha_v\beta_1$ integrin-mediated TGF- β 1 activation (IC₈₀ ~ 2300 ng/mL) for approximately 8 hours and the target IC₅₀ (~ 500 ng/mL) for 24 hours. PLN-74809 160 mg is the highest dose evaluated in the ongoing dose ranging Study PLN-74809-IPF-202.

To complement prior and ongoing safety evaluations, the safety, tolerability and PK of PLN-74809 in participants with IPF, with or without co-administration with SoC (pirfenidone or nintedanib) will also be assessed. The proposed randomized, double-blind

study design allows a reduction in bias in the assessment of type 1 collagen expression and of drug safety and tolerability. Stratification for background treatment with SoC will ensure a similar proportion of participants on SoC in each treatment group. The proposed sample size and 12-week treatment duration are expected to provide meaningful PK information in the IPF population, comparing PLN-74809 to placebo. The proposed randomization strategy in this exploratory study, 2:1 (PLN-74809 : placebo), will allow for determination of change in type 1 collagen deposition over 3 months and the impact of PLN-74809, which is expected to lead to decreased type 1 collagen expression within the lung based on localized inhibition of TGF- β signaling.

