6.5 Blinding

The placebo treatment will resemble the active treatment for tablet shape, size and color. This ensures that the participant, Investigator, clinical site study staff, and Sponsor study team directly involved in trial conduct are unaware of the treatment allocation during the conduct of the study. The PLN-74809 or placebo will be provided as blinded kits and will be assigned to participants using a randomization code.

Procedures will be in place to allow prompt breaking of the blind by the investigator if needed for the safety management of a participant. Unblinding at the study site for any other reason will be considered a protocol deviation. The investigator is strongly encouraged to contact the sponsor Study Director before unblinding any participant's treatment assignment, but must do so within one working day after the event. A written explanation of the reason for unblinding should be provided to the sponsor within 24 hours of breaking the blind. Refer to the IRT User Guide for a description regarding how investigators may access treatment information via the IRT system.

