7.10 Pharmacodynamic Assessments

7.10.1 PET/MRI Imaging for the Assessment of Type 1 Collagen Deposition

All PET/MRI will be performed at the Martinos Center for Biomedical Imaging at Massachusetts General Hospital. PET imaging will be performed at prespecified times according to the Schedule of Events ([Appendix 1](#)) using the collagen-targeted tracer, ⁶⁸Ga-CBP8 as synthesized at the Martinos Center for Biomedical Imaging, and following predefined instructions as detailed in the Radiology Manual for the study. The radiochemical dose is up to 12.9 mCi per administration; but in practice, the dose averages to 5.5 mCi per subject. The total amount of radiation exposure from the PET/MRI is equal to a whole-body exposure up to 22 mSv (11 mSv per administration of ⁶⁸GaCBP8). Blood samples will be obtained prior to each PET/MRI and will be stored for future analyses. Details for blood sample collection and processing are detailed in the Radiology Manual.

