7.12 Exploratory Efficacy Assessments

7.12.1 Spirometry

Absolute FVC volume and FVC percent of predicted will be assessed by spirometry at screening and at the timepoints specified in the Schedule of Events ([Appendix 1](#)). A historical value may be used if it has been completed within 1 month from the Baseline visit.

FEV1 will be assessed by spirometry at screening. A historical value may be used if it has been completed within 1 month from the Baseline visit.

7.12.2 *Patient-reported Outcome (PRO)*

Study participants will respond to a VAS for cough severity at the timepoints specified in the Schedule of Events ([Appendix 1](#)).

7.13 *Concomitant Medication and Adverse Event Assessments*

At each study visit, participants will be asked about how they are feeling and what medications they are taking (have started/stopped, adjusted dose, etc.).

7.14 *Missed Assessments*

Missed assessments will be reported as such and will not be imputed.

7.15 *Appropriateness of Measurements*

Collagen accumulation within the lungs of patients with fibrotic lung disease, particularly those with IPF, is the hallmark of disease progression and associated with substantial mortality. The changes in the PET ligand ^{68}Ga -CBP8 correlate with disease progression and may be a more sensitive measure of active disease, with ^{68}Ga -CBP8 preferentially binding to recently synthesized collagen over mature, organized collagen. Consistent with the mechanism of action of PLN-74809, changes in the PET ligand ^{68}Ga -CBP8 will support the role of ^{68}Ga -CBP8 as an important biomarker of disease activity, as well as evidence of PD effect and efficacy of PLN-74809 (decrease in collagen levels) in participants with IPF.

Collection of AEs, safety labs, vital signs, physical examinations and ECG recordings are standard well-established parameters to assess the safety and tolerability of pharmacological agents.

PK samples will be analyzed according to predefined validated analytical methods to assess the concentrations of PLN-74809 in plasma.

FVC is a standard measure collected according to current ATS guidelines for the measurement of IPF progression. The VAS scale for the assessment of cough will follow recommendations from the ERS Guidelines ([Morice et al, 2007](#)).

When available, appropriate standard guidelines will be used.

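### The Protocol has the primary-endpoint PET/MRI scans read unblinded in a double-blind trial, and neither document says that contouring or SUV quantification is masked to arm

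*Protocol*

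**What the plan says.** Protocol Section 12.5.1, on the primary pharmacodynamic endpoint, states: "PET/MRI scans will be interpreted by American Board of Nuclear Medicine (ABNM)-certified nuclear medicine physicians in an unblinded manner". The Synopsis, under Statistical Methods, repeats it ("nuclear medicine physicians in an unblinded manner"). Neither place defines the term.

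The next sentence of 12.5.1 covers contouring and names nobody: "Lung contours will be generated from baseline and post-treatment PET/MRI". SAP 5.2.4 assigns SUV quantification to the imaging laboratory, using software, and does not mention masking.

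Elsewhere the Protocol describes a blinded trial:

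- Section 3.1: "randomized, double-blinded, placebo-controlled study to evaluate type 1 collagen deposition in the lungs".
- Section 3.2, on why the design was chosen: "study design allows a reduction in bias in the assessment of type 1 collagen expression".
- Section 6.5: "the participant, Investigator, clinical site study staff, and Sponsor study team directly involved in trial conduct are unaware of the treatment allocation". Image readers and the imaging laboratory are not named. Unblinding at the site for any reason other than a participant's safety counts as a protocol deviation.

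Section 7.10.1 sends the imaging procedures to a separate document ("following predefined instructions as detailed in the Radiology Manual for the study"), which was not available for this review. The SAP's list of changes from the Protocol (SAP Section 9) clarifies the primary endpoint but leaves the unblinded-reading sentence alone.

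**The concern.** In a placebo-controlled trial, reading scans unblinded would ordinarily mean knowing the treatment arm. Section 3.2 presents the double blind as protection for the collagen assessment. Section 12.5.1 then appears to remove that protection from the same assessment.

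The result will carry weight. Section 7.15 says tracer changes will serve "as well as evidence of PD effect and efficacy of PLN-74809 (decrease in collagen levels) in participants with IPF". SAP 5.11.1 reports the PLN-74809 minus placebo difference with an SE, 95% CI and P-value, and SAP 5.11 sets a two-tailed 5% level. If whoever draws contours, sets region boundaries or judges scan quality knows the arm, those choices can shift one arm relative to the other. The shift enters the estimated difference directly, and the ANCOVA cannot remove it. With 8 and 4 participants, little in the data would reveal it.

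**Working it through.** **Text check.** The possible meanings of the sentence, set against the rest of the plan:

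| Meaning of unblinded | Fit with the rest of the plan | Effect on the arm difference |
|---|---|---|
| Knows treatment arm | Contradicts Sections 3.1 and 3.2; contradicts 6.5 too if readers are clinical site study staff, which is not stated | Can bias it, if the same people contour or quantify, or influence those who do |
| Knows scan order | Compatible with the double blind, but not stated | None from a shift common to both arms |
| Knows clinical data | Compatible, but not stated | Depends on whether the data hint at arm |
| Slip for blinded | Compatible | None, once corrected |

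The sentence needs correcting under every row. Only the first makes it a design flaw.

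**Illustration of size.** The plan gives no reader-effect size, SD or power figure, so there is nothing of its own to reproduce beyond the allocation: 12 × 2/3 = 8 and 12 × 1/3 = 4.

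Inputs from the documents:

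- 8 versus 4 participants (Protocol 12.2).
- ANCOVA of change on baseline and treatment (SAP 5.11.1).
- Two-sided 5% (SAP 5.11).

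Assumptions:

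- All 12 participants are evaluable.
- Baseline and residuals are normal with unit variance.
- The true arm difference is 0.
- A reading shift of *b* residual SD is added to one arm.

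*Analytic check, no baseline imbalance.* Error df = 12 − 3 = 9. SE = √(1/8 + 1/4) = √0.375 = 0.612 SD. The 95% CI half-width is 2.262 × 0.612 = 1.385 SD. The rejection rate comes from a noncentral t with 9 df and noncentrality *b*/0.612.

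*Simulation, random baseline imbalance.* 400,000 trials per setting, with the ANCOVA above. The true difference is 0, so CI coverage is 1 minus the rejection rate.

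| Assumed arm shift (SD) | Noncentrality | Rejection, analytic | Rejection, simulated | CI coverage, simulated |
|---|---|---|---|---|
| 0 | 0 | 5.0% | 5.0% | 95.0% |
| 0.25 | 0.41 | 6.6% | 6.4% | 93.6% |
| 0.50 | 0.82 | 11.3% | 10.7% | 89.3% |
| 0.75 | 1.22 | 19.5% | 18.3% | 81.7% |
| 1.00 | 1.63 | 30.9% | 28.6% | 71.4% |

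The mean simulated half-width is 1.46 with the residual SD fixed at 1. It is about 1.42 when the SD is estimated (1.464 × 0.973, the small-sample factor for 9 df).

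*Standard-of-care term.* SAP 5.11.1 defines a variable for standard-of-care use beside its example code but leaves it out of the model description. Fitting it as well (8 df, assuming 9 of 12 on standard of care, split 6 and 3) gives 10.6% at 0.5 SD and 27.7% at 1.0 SD, so the picture does not change.

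*Common shift.* Moving all Week 12 values in both arms by 0.5 or 1.0 SD gives rejection rates of 5.0% and 5.1%. The shift cancels in the arm contrast.

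**The case against.** The best defence is that the sentence is ambiguous and not shown to be wrong.

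- **Other provisions point away from arm knowledge.** Section 6.4 assigns treatment in a blinded manner through IRT. Section 6.5 makes non-safety unblinding at the site a deviation. No passage gives readers a route to the codes. Comparing baseline with post-treatment scans, as 12.5.1 describes, also fits readers who know only the timepoint.
- **The interpretation step may not produce the endpoint.** SAP 5.2.4 has the SUVs computed by software in the imaging laboratory, and the analysed metric is a top-quartile mean, not a reader score. The physicians' read could be a separate clinical one.
- **The Radiology Manual may already require masking.**
- **The shift sizes are invented.** The study is exploratory, and Protocol 12.1 says no hypothesis is tested, so false-positive rates are not the main issue.

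Much of this stands. The meaning cannot be settled from the documents, no passage links interpretation to the SUVs, and the illustration shows only what a given shift would do. But no alternative rescues the sentence. A slip must be corrected, knowledge of scan order must be stated, and a manual that requires masking would contradict what the Protocol says in two places. Software limits discretion without removing it, since the SUVs come from contoured lungs and neither document says the contouring is automated. The exploratory label lowers the stakes of a decision but does not take bias out of an estimate and its interval.

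**Conclusion.** The concern holds, and the text must be fixed before the primary result is relied on. That the Protocol says this twice, and that masking of contouring and quantification is unstated in both documents, is certain. That readers were meant to know treatment arm is the natural reading but is not proven, so confidence in that part is medium.

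The size of any bias cannot be estimated from the documents. If it arises, the bias in the estimated difference equals the differential shift, and interval coverage falls below 95%. Under the assumed shifts of 0.25 to 1.0 SD, coverage runs from 93.6% down to 71.4%. As the study tests no hypothesis, a biased estimate and interval matter more than the P-value. The conclusion rests on the conflict between the passages and does not depend on the simulation.

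**What to change.** 1. In Section 12.5.1 and the Synopsis, replace the unblinded-reading phrase with a statement such as: *masked to treatment arm; contours and SUVs are locked before unblinding*. Apply it to readers and to anyone who contours or quantifies scans.
2. Add these people to the blinded parties in Section 6.5.
3. Put the same sentence in SAP 5.2.4, and check that the Radiology Manual agrees.
4. If the intended meaning was only scan order or clinical data, say so beside the arm-masking statement.
5. If reads were already made with knowledge of arm, disclose this as a limitation of the primary result. Re-contouring of coded scans in random order is optional.

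The cost is wording in three Protocol places and one SAP section, plus minor coding work for about 24 scans (12 participants × 2). No re-read is required.
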